- vi) A significant improvement in symptoms of angina as measured by the Rose Questionnaire
- vii) A significant improvement in quality of life as measured by the LASA Questionnaire, symptoms of depression as measured by the PHQ-9 Questionnaire, and symptoms of stress as measured on the Perceived Stress Scale
- viii) No significant difference in blood levels of creatinine kinase across time
- viii) A significant improvement in sensorimotor characteristics (visual-motor reaction time, peak knee muscular force, muscular force steadiness, standing balance, and overhead squatting posture)
- ix)

Methods

Trial Design

This study will consist of a **blinded randomized controlled prospective study design**, and will include 80 healthy individuals who are employees at Mayo Clinic, Rochester MN.

Excluded subjects will consist of:

- Subjects under the age of 18
- Pregnancy/or suspected pregnancy
- Subjects with a history of liver or kidney disease, acute illness, taking medications (such as glucocorticoids)
- Subjects who have conditions (such as chronic inflammatory muscular diseases or Cushing's syndrome) that affect muscle mass

- Individuals with pacemakers and implantable cardiac defibrillators
- Individuals who conduct any other type of resistance training (> 45 minutes/week)
- Individuals who have regular “high” alcohol consumption (> 80g/day on 5 days a week), or are under acute influence of alcohol, drugs narcotics, and/or painkillers
- Subjects unable to consent to or participate in the 16-week EMS intervention or be available for follow up (1).
- Subjects who report recent surgeries
- Cardiac arrhythmias
- Active medical implants
- Epilepsy
- Seizures
- Severe circulatory disorders
- Arterial circulatory disorders
- Strong bleeding tendencies (hemophilia)
- Bleeding
- Abdominal wall hernia
- Inguinal hernia
- Tuberculosis
- Tumor diseases
- Arteriosclerosis in advanced stage
- Severe neurological disorders
- Diabetes mellitus
- Febrile diseases
- Acute bacterial or viral infections
- Liver diseases
- Kidney diseases
- Cardiovascular diseases
- Coronary heart diseases
- Infected or wounded areas of the skin
- Skin cancer
- Rhabdomyolysis

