This will be a randomized controlled trial in which there will be an interventional group and a control group into which individuals will be randomly assigned in a 1:1 ratio. We will match individuals, a priori, as best as possible on age (within 5 years) and sex. Baseline, demographic and risk factor distribution will be outlined in Table 1 of our analyses. The following parameters will be measured in all subjects at baseline, and at 16-weeks follow-up (immediately after completing training in either study protocol depending on which group the participant is in): peripheral endothelial function measured with RH-PAT using EndoPAT; body weight and body mass index; waist circumference; blood pressure; total cholesterol, low and high density

lipoprotein cholesterol and triglycerides, fasting blood glucose and HbA1c; high sensitivity-CRP, uric acid, fibrinogen, homocysteine and lipoprotein A; percentage body fat; maximum strength and maximum power in leg press; VO₂ maximum, maximal heart rate, and scores measured on the Rose questionnaire, LASA questionnaire, PHQ-9 questionnaire and Perceived Stress Scale. In addition, serum creatinine kinase will be measured at baseline, 8 weeks and 16 weeks.

We will compare values of each parameter between groups at baseline and after 16-weeks using unmatched analyses (using Student's t-test when comparing the aforementioned measures as continuous variable and using Chi-squared test when characterizing variables in categories of normal vs. abnormal). We will also assess for differences in the value of each parameter within groups between baseline and 16-weeks follow-up using matched analyses (using Student's paired t-test when comparing the aforementioned measures as continuous variable and McNemar's test when characterizing variables in categories of normal vs. abnormal). Lastly, we will compare the differences between baseline and 16-weeks follow-up for each parameter between groups using unmatched analyses (using the student t-test when comparing the aforementioned measures as continuous variable and using Chi-squared test when characterizing variables in categories of normal vs. abnormal).

Clinical Significance

Cardiovascular disease (CVD) is the primary cause for morbidity, mortality, and the associated rising health care costs in the world (21). According to 2012 statistics, poor diet, smoking, and

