An important issue that has arisen with EMS training is the potential risk of elevation in blood creatinine kinase levels. Studies investigating the effects of EMS on creatinine kinase levels have shown that the electrical stimulus from EMS can cause significantly more stress to the muscular system and therefore could lead to higher creatinine kinase levels compared to voluntary muscle contraction exercise (88, 91). Indeed, due to the ability to innervate large muscle areas simultaneously with dedicated individual intensity to each muscle group, EMS can be associated with potential muscle injury. One study showed that, compared to traditional strength training, the stress on the muscular system is about 40% higher after intensive EMS (88). The authors arrived at the conclusion that the level of stimulation intensity is responsible for the elevation in creatinine kinase, while the duration of stimulation had no influence. The authors also showed that subjects still exhibited high values after long periods ranging from 24 hours to 4 days. Further stimulation within this time of decomposition would result in a cumulative rise in creatinine kinase levels (88), which in turn could overstress the muscular system further. Further, one study in which whole body EMS was implemented to the point of exhaustion in healthy novices confirmed very high elevations in creatinine-kinase levels. Although this study did not detect any of the reported clinical consequences of this “severe” rhabdomyolysis, in less fit subjects who are neither optimally prepared nor supervised, initial whole body EMS to exertion may have more far-reaching consequences. Consequently, EMS requires a greater interval between training sessions to prevent overstressing the muscular system and to ensure strength adaptations compared to conventional training. Of note, a subsequent whole body EMS conditioning phase of 10 weeks completed by a second EMS test application to exhaustion demonstrated creatinine-kinase peaks in the range of conventional resistance exercise

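### CK is analysed only by arm means and a normal/abnormal split, so a few severe individual elevations can pass as the hypothesised non-significant result

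*Combined protocol and SAP*

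**What the plan says.** All references are to the combined protocol and SAP.

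- **Sampling.** Statistical Analysis: "In addition, serum creatinine kinase will be measured at baseline, 8 weeks and 16 weeks". The Schedule of events agrees.
- **Tests.** The same section sets one scheme for all outcomes: "We will compare values of each parameter between groups at baseline and after 16-weeks using unmatched analyses". Continuous values are handled "using Student's t-test when comparing the aforementioned measures as continuous variable" and categories "using Chi-squared test when characterizing variables in categories of normal vs. abnormal". Within arms the counterparts are the paired t-test and McNemar's test. Changes from baseline are compared between arms by t-test or chi-squared. These tests name baseline and week 16; none is assigned to the week-8 CK.
- **Hypothesis.** The CK item in the Hypotheses section reads "No significant difference in blood levels of creatinine kinase across time". No margin is given.
- **Known hazard.** Efficacy and Safety Considerations reports that a study of whole body EMS taken to exhaustion in novices "confirmed very high elevations in creatinine-kinase levels", and discusses this as severe rhabdomyolysis.
- **Size.** Trial Design: the study is randomised "and will include 80 healthy individuals who are employees at Mayo Clinic, Rochester MN". Statistical Analysis: "individuals will be randomly assigned in a 1:1 ratio".

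The document gives no alpha, CK cut-off, listing or count of high individual values, maximum or percentile summary, or adverse-event analysis.

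**The concern.** The worrying CK event is a very high value in a particular person. An arm mean does not show it. A few huge values raise the standard deviation along with the mean, so the t-statistic stops growing however high those values go. One cut at normal does not show it either, because a slightly raised value and a severe one count the same.

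This matters more for CK than for the other laboratory outcomes. CK is the only marker of muscle damage in the laboratory schedule, and its hypothesis is worded so that a non-significant test looks like confirmation. A trial with two or three severe elevations in the EMS arm could satisfy that hypothesis without any planned output showing them.

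**Working it through.** **Inputs.** 80 participants at 1:1 gives n = 80/2 = 40 per arm, with no dropout assumed. Two-sided 5% is assumed. The total of 80 comes without alpha, power, effect size or SD, so it cannot be reproduced.

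**1. Ceiling of the t-test.** Let k EMS participants share a value M so large that all other variation is negligible, with no extreme control.

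- Mean difference = kM/n.
- Pooled variance = k(1 − k/n)M²/(2n − 2).
- Squared standard error = pooled variance × 2/n.
- M cancels, leaving t = √[k(n − 1)/(n − k)].

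For k = 3: √(3 × 39/37) = 1.778, below the critical value 1.991 (78 df). The paired t-test in the EMS arm has the same limit on 39 df (k = 3: p = 0.083).

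**2. Chi-squared, k/40 versus 0/40.** The uncorrected statistic is 80k/(80 − k). For k = 3: 240/77 = 3.12, below 3.84.

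| k | t limit | p (t) | χ² | p (χ²) | p (Yates) | p (Fisher) |
|---|---|---|---|---|---|---|
| 1 | 1.00 | 0.320 | 1.01 | 0.314 | 1.00 | 1.00 |
| 2 | 1.43 | 0.156 | 2.05 | 0.152 | 0.474 | 0.494 |
| 3 | 1.78 | 0.079 | 3.12 | 0.078 | 0.239 | 0.241 |
| 4 | 2.08 | 0.041 | 4.21 | 0.040 | 0.124 | 0.116 |
| 5 | 2.36 | 0.021 | 5.33 | 0.021 | 0.065 | 0.055 |
| 6 | 2.62 | 0.011 | 6.49 | 0.011 | 0.034 | 0.026 |

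The break lies between three and four cases. With Yates or Fisher it moves to six. McNemar in the EMS arm with three new abnormal values and no other changes gives p = 0.083 uncorrected and 0.25 exact.

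**3. When the ceiling does not bind.** These simulations used 20,000 runs, except the chi-squared results under a general shift of 1.5 times, which used 3,000. CK is assumed log-normal with log-SD 0.5, and the upper reference limit is 2.5 times the median.

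- *t-test alone, three EMS values all at a fixed multiple of the median:* significant in 18% of runs at 5-fold and at 10-fold, 8% at 20-fold, 0.1% at 50-fold and 0% at 100-fold. Beyond 10-fold, the more severe the elevation, the less often the test detects it.
- *Both tests, three EMS participants' own values multiplied by 10 to 50, no other shift:* at least one test is significant in about 23% to 27% of runs. Most of this is chi-squared, helped by mildly abnormal values among the other EMS participants.
- *General shift added:* if the rest of the EMS arm also rises 1.5 times, chi-squared is significant in about 80% of runs.

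**4. What would make detection harder.** Four unequal extremes in the ratio 1 : 0.5 : 0.3 : 0.2 give p = 0.085 by t-test. With one or two abnormal controls, uncorrected chi-squared needs six or eight abnormal EMS participants.

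**5. What 40 EMS participants can exclude.** For 0/40 the exact (Clopper–Pearson) upper 95% limit is 1 − 0.025^(1/40) = 8.8%. At a true risk of 5%, P(at least one case) = 1 − 0.95^40 = 0.87 and P(three or fewer) = 0.86.

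**The case against.** The ceilings are limits for very extreme values on a quiet background, so they do not make significance impossible. The background section also describes a general effect, with EMS stressing muscle more than voluntary contraction and by about 40% in one study. Three extreme participants among 37 who match controls is a scenario that the documents do not describe. If the EMS arm also shifts by 1.4 times (illustrative only, since the 40% refers to muscular stress and not to CK), at least one test is significant in about 70% to 90% of runs.

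This stands as a limit on the claim. A reader might infer that neither test can ever be significant with three or fewer severe cases. The documents do not support that. They fix no alpha (one-sided, the t limit at three cases gives p = 0.040) and no CK cut-off, and the categorical test counts every abnormal value. Unequal dropout matters too: with 30 EMS and 40 control completers, three cases give p = 0.041 by chi-squared.

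A reader might also infer that the sponsor will report EMS as harmless to muscle. No section says so. The documents set no rule for reporting individual CK values and do not rule out listing them.

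Two further objections bear on the remedy, and both are right. The 8.8% limit follows from the sample size, so a new analysis cannot improve it. Post-baseline CK is drawn only at weeks 8 and 16, while the background says that raised values last 24 hours to 4 days, so no listing can show peaks between visits.

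None of this answers the main point: a significant mean or normal/abnormal test would still not show whether anyone had a severe value.

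**Conclusion.** The concern holds in a conditional form. At two-sided 5%, with 40 completers per arm, three or fewer very extreme EMS values and all other values normal and alike, neither planned between-arm test reaches significance (p = 0.079 and 0.078 at three cases, which is 7.5% of the arm). With ordinary background variation, three elevations of 10- to 50-fold go undetected by both tests in roughly three quarters of runs under the stated simulation assumptions. Detection becomes likely only if CK rises across the EMS arm.

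The defect in the choice of summary needs none of these conditions. An arm mean and a single cut at normal do not display individual severe elevations, and the CK hypothesis invites a non-significant result to be read as reassurance. The plan should be changed, but the primary aim is not affected.

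**What to change.** Add to the Statistical Analysis section:

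1. A listing of every participant's CK by arm and visit, including week 8.
2. A table, by arm, of the number whose highest scheduled post-baseline CK exceeds multiples of the laboratory's upper reference limit, with exact 95% confidence intervals. The sponsor fixes the multiples before unblinding.
3. Multiples of the participant's own baseline as a secondary display only, because the Schedule of events places both EMS exercise and the baseline CK on Day 0 without giving their order.
4. A statement that a non-significant mean or normal/abnormal comparison will not be read as absence of CK harm. It should add that 0 of 40 still leaves an upper 95% limit of about 8.8%, which applies to the scheduled draws and not to peaks between visits.

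The cost is one listing, one table and a few lines of text, all from data already collected. No visit or procedure changes. The safety statement becomes less favourable: at best an upper limit of about 9%, in place of no significant difference.

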Previous studies have demonstrated dependence of the RH-PAT score on nitric oxide, confirming that reported RH-PAT scores indeed reflect changes in nitric oxide– dependent endothelial function, rather than neurohormonal activation (15). The reactive hyperemia protocol will consist of a 16-minute reactive hyperemia test, in the following sequence. A five-minute baseline measurement, after which a blood pressure cuff on the test arm will be inflated to 60 mmHg above baseline systolic blood pressure, or at least 200 mmHg for five minutes (occlusion of pulsatile arterial flow will be confirmed by the reduction of the PAT tracing to zero) after which, the cuff will be deflated, and the post-deflation PAT tracing will be recorded for an additional six minutes. The ratio of the PAT signal after cuff release compared to baseline will be calculated through a computer algorithm automatically normalizing for baseline signal, and indexed to the contralateral arm. The calculated ratio reflects the RH-PAT score (scores below 1.7 will be considered consistent with abnormal peripheral endothelial function).

Although RH-PAT scores may not be the gold standard for endothelial function, several studies have shown good correlation between these methods and more widely accepted methods of

endothelial function testing, such as intra-arterial acetylcholine infusion and brachial artery Doppler ultrasound following reactive hyperemia (11, 13, 14).

Laboratory Testing: Laboratory testing will be undertaken in all participants at baseline, and at 16-weeks follow-up in both the intervention and control group. Venous blood will be drawn for high-sensitivity CRP, uric acid, fasting glucose, HbA1c, lipid panel, lipoprotein A, homocysteine and fibrinogen. For patients in both groups, venous blood will also be tested for creatinine kinase levels at baseline, 8-weeks (halfway into the training programs), and 16-weeks (after completing each respective training program for both groups). A blood sample of approximately 30 mL will be drawn and all samples will be sent to the Mayo Clinic central laboratory for analysis.

Body Weight, Height, and Waist Circumference: Body height, weight and waist circumference will be measured using calibrated devices. Body mass index will be calculated as mass (kg)/height (m²).

VO2 MAX and Maximal Heart Rate: This will be tested using exercise treadmill testing in the conventional manner.

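### The chi-squared test on between-group differences in normal/abnormal status has no defined table and ignores baseline status, so it mixes baseline prevalence with the treatment effect

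*Combined protocol and SAP*

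**What the plan says.** The Statistical Analysis section sets out three comparisons for every listed parameter:

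1. Between groups at baseline and at week 16, by t-test or chi-squared test.
2. Within groups, by paired t-test or McNemar's test.
3. Between groups on the change: "Lastly, we will compare the differences between baseline and 16-weeks follow-up for each parameter between groups using unmatched analyses". The continuous version is done "using the student t-test when comparing the aforementioned measures as continuous variable" and the categorical version "using Chi-squared test when characterizing variables in categories of normal vs. abnormal".

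The chi-squared wording appears in both the first and the third comparison. This point concerns the third.

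For the primary measure, the Peripheral Endothelial Function section supplies a cut: "scores below 1.7 will be considered consistent with abnormal peripheral endothelial function". On balance between arms, participants are "randomly assigned in a 1:1 ratio", and the plan adds "We will match individuals, a priori, as best as possible on age (within 5 years) and sex". Baseline normal/abnormal status is not a balancing factor, and no planned test adjusts for it. The Trial Design section says the study "will include 80 healthy individuals who are employees at Mayo Clinic, Rochester MN", which is 40 per arm.

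**The concern.** The difference of a continuous score is a number, and a t-test on it is well defined. The difference of a two-level status is not a two-level variable. It could be tabulated as improved/unchanged/worsened, as improved versus not, or as changed versus not, and these are different tests. The plan names none of them.

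Under any of these tables the result depends on baseline. A participant who starts normal cannot improve, and one who starts abnormal cannot worsen. If one arm happens to start with more abnormal participants, it will show more improvers even when the treatment does nothing. With 40 per arm and balancing attempted only on age and sex, such an imbalance is realistic. At stake is a categorical result, for RH-PAT at the 1.7 cut and for every other dichotomised parameter, that could be read as a treatment effect when it partly reflects who started abnormal.

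**Working it through.** **Inputs from the documents.** 80 participants, 1:1, so 40 per arm; RH-PAT cut 1.7. The figure of 80 comes with no alpha, power, effect size or SD, so there is no sample-size calculation to reproduce.

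**Inputs assumed, because the documents give none.** Two-sided alpha 0.05; no dropout; RH-PAT SD 0.5; baseline mean 2.0 (or 2.3); true gain 0.3; baseline-to-week-16 correlation 0.5 to 0.7. A wider grid uses 15% to 50% abnormal at baseline, correlation 0.3 to 0.8 and a uniform shift of 0.4 to 0.8 SD.

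**Step 1. Dependence on baseline prevalence.** P(improved) = P(abnormal at baseline) × P(conversion to normal). Take 30% conversion in both arms, so no treatment effect, and baseline prevalences of 20% and 40%. The improved shares are 0.20 × 0.30 = 6% and 0.40 × 0.30 = 12%.

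**Step 2. Expected counts under no effect.** Suppose 60% of abnormal participants stay abnormal and 15% of normal participants become abnormal, in both arms. Start with 8 of 40 abnormal in the control arm and 16 of 40 in the EMS arm.

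| | Control | EMS |
|---|---|---|
| Improved | 8 × 0.40 = 3.2 | 16 × 0.40 = 6.4 |
| Worsened | 32 × 0.15 = 4.8 | 24 × 0.15 = 3.6 |
| Abnormal at week 16 | 8 × 0.60 + 4.8 = 9.6 | 16 × 0.60 + 3.6 = 13.2 |

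The change table leans towards EMS and the unadjusted week-16 table leans against it, although nothing has happened. Within each baseline stratum the arms are identical (60% and 60%, 15% and 15%), which is why stratifying removes the distortion.

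**Step 3. Rejection rates under no effect, at the Step 2 rates (simulation).**

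| Abnormal at baseline, control vs EMS | Three-level table | Improved vs not | Cochran-Mantel-Haenszel (CMH) |
|---|---|---|---|
| 12 vs 12 | 2.9% | 2.4% | 4.9% |
| 9 vs 15 | 6.7% | 9.0% | 4.7% |
| 8 vs 16 | 11.0% | 15.5% | 5.0% |

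In the RH-PAT model (mean 2.0, correlation 0.6), the three-level test rejects 2.7%, 5.8% and about 13% of the time at imbalances of 0, 5 and 8. CMH stays at about 5%. The planned unadjusted week-16 test rejects about 11% of the time at an imbalance of 8.

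**Step 4. How often such an imbalance occurs.** P(abnormal) = Φ((1.7 − 2.0)/0.5) = Φ(−0.6) = 27.4%. The SD of the difference in counts is √(2 × 40 × 0.274 × 0.726) = 3.99. With continuity correction, P(|difference| ≥ 8) ≈ 2 × [1 − Φ(7.5/3.99)] = 2 × [1 − Φ(1.88)] ≈ 6%. Averaged over randomisation, type I error is about 4% to 6%.

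**Step 5. Sparse cells.** In the RH-PAT scenarios under no effect, at least one expected count in the three-level table is below 5 in 58% to over 99% of trials. This makes the test slightly conservative on average; it does not inflate it.

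**Step 6. Power (simulation, uniform gain 0.3, correlation 0.5 to 0.7).**

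| | Three-level change | Week-16 chi-squared (planned) | CMH |
|---|---|---|---|
| Mean 2.0 | 25–27% | 44–46% | 46–52% |
| Mean 2.3 | 10–12% | about 29% | 26–28% |

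Across the wider grid, the ratio of three-level power to CMH power has median 0.54 (range 0.36 to 0.75). For improved versus not the median is 0.38, and for changed versus not 0.15. If only participants abnormal at baseline respond, the loss largely disappears: about 12% versus 12% in the RH-PAT model at mean 2.0, and three-level ratios of 0.81 to 1.11 with fixed conversion rates.

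For comparison, the SD of the continuous change is 0.5 × √(2(1 − ρ)), which is 0.50 at ρ = 0.5 and 0.39 at ρ = 0.7. The standardised effects are 0.60 and 0.77, and the planned t-test on change has about 76% to 93% power.

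**The case against.** Three stronger readings are tempting, and the documents do not support them.

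**That the planned test has half the power of a proper one.** This needs a three-level table and a treatment that shifts everyone. The plan fixes neither. The ratio moves from well under a half to no loss, depending on the table and on who responds.

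**That the false-positive rate is 13%.** That figure is conditional on an imbalance with about a 6% chance. Over all randomisations the rate is near 5%, so the test is not invalid.

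**That the primary endpoint is in danger and true effects will be missed.** The primary aim names endothelial function measured by EndoPAT and does not mention the 1.7 cut. The same section plans a t-test on the continuous change, which is far more powerful than any dichotomised test here. It also plans a chi-squared test of week-16 status, which already recovers most of the power of the stratified test.

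These replies limit the point but do not remove it. The plan does not say which comparison takes precedence, so the categorical change test could be the one reported. The week-16 test is also unadjusted and, at the same imbalance, rejects about 11% of the time. Leaving the table undefined does not help either: under a uniform shift, the other two tables have lower median power than the three-level one.

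**Conclusion.** The point stands as a modest one. The categorical change comparison is undefined and unadjusted for a baseline status that is already collected, so its result mixes baseline prevalence with the effect. The main benefit of adjusting is protection against chance imbalance: about 5% false positives instead of about 13% (three-level change) or 11% (unadjusted week-16 status) when one arm starts with 8 more abnormal participants.

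The power argument is secondary. A three-level change table has roughly 0.4 to 0.75 of the stratified test's power under a uniform shift, with little or no loss if only baseline-abnormal participants respond. Against the week-16 test already planned, the gain is about 0 to 7 points in the RH-PAT scenarios. It is somewhat larger, about 10 points, at 40% to 50% abnormal with correlation 0.7 and a shift of 0.63 SD.

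Every figure rests on assumed means, SDs, correlations and effects. The dependence on baseline prevalence does not; it follows from how a change in status is defined.

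**What to change.** In the closing sentence of the Statistical Analysis section, replace the chi-squared test on differences with a between-arm comparison of week-16 normal/abnormal status adjusted for baseline status. Use a Cochran-Mantel-Haenszel test stratified by baseline status, or logistic regression with baseline status as a covariate, and the exact version when any expected count is below 5. Label it supportive to the continuous analysis, and say that it takes precedence over the unadjusted week-16 chi-squared test.

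The cost is one changed sentence and no new data. The downside is a possible slight loss of power when abnormal status is rare: at mean 2.3, where Φ((1.7 − 2.3)/0.5) = Φ(−1.2) ≈ 12% start abnormal, power is 26–28% against about 29% unadjusted.
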